#### **9.5.1.3. Exploratory Analyses**

Not applicable.

#### **9.5.1.4. Multiplicity Adjustment**

Not applicable.

#### **9.5.2. Safety Analyses**

Safety analyses in general will be descriptive and will be presented in tabular format with the appropriate summary statistics. Safety analyses will be performed using the Safety Analysis Set and subjects will be analyzed according to their actual treatment received.

The overall study period will be divided into 3 mutually exclusive segments for statistical analysis and reporting purposes:

- Pre-treatment period: from date of informed consent (inclusive) to the start date of study treatment -1

- On-treatment period: from the start date of study treatment (inclusive) to 47 days after the end date of study treatment (inclusive)
- Post-treatment period: starting from 48 days after the end date of study treatment.

Only data from the on-treatment period will be summarized, unless otherwise specified, except in cases where data from the pre-treatment period will be used for baseline determination.

### **Adverse Events**

Adverse events will be coded using MedDRA and graded using NCI-CTCAE v5.0.

A TEAE is defined as an AE with a start or worsening date during the on-treatment period.

The TEAEs will be summarized using system organ class (SOC) and/or PTs. Additional summaries will be provided by the worst CTCAE grade, relationship to the study treatment (ie, regardless of relationship to study drug, study drug related), seriousness, actions taken with study treatment (ie, associated with dose reduction, dose interruption, study treatment discontinuation), and fatality.

If a subject reports more than one AE with the same PT, the AE with the worst CTCAE grade will be presented. If a subject reports more than one AE within the same primary SOC, the subject will be counted only once with the worst CTCAE grade at the SOC level, where applicable.

AESIs will also be summarized.

All AEs will be listed, including, but not limited to, verbatim term, PT, SOC, CTCAE grade, relationship to study drug, start and end dates, and outcome. Non-TEAEs will be flagged in the listing.

SAEs starting or worsening after the on-treatment period, if reported as related to the study treatment, will be summarized.

### **Clinical Laboratory Evaluation**

Descriptive statistics will be provided for selected clinical laboratory test results (hematology and chemistry) and changes from baseline by scheduled time of evaluation, including the EOT Visit.

Abnormal clinical laboratory results will be graded according to NCI-CTCAE v5.0, if applicable. A shift table, presenting the 2-way frequency tabulation for baseline and the worst post-treatment value according to the NCI-CTCAE grade, will be provided for selected clinical laboratory tests. Abnormal clinical laboratory test results that are deemed of clinical significance or of Grade 3 or 4 will be listed.

### **ECG**

A listing of ECG data will be provided.

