
To assess the safety and tolerability of patritumab deruxtecan in subjects with metastatic or locally advanced NSCLC with an activating EGFR mutation (exon 19 deletion or L858R)
	
Title: Safety during the study*
 
Description: Descriptive statistics of safety endpoints
 
Time frame: From the time the subject signs the main study ICF and up to 40 (+ 7) days after the last dose of study drug (ie, 5 half-lives of the ADC/the follow-up period).
 
*Although this is a secondary objective, this is a primary outcome measure.
	
Incidence of TEAEs, SAEs, AESIs (ILD and elevation of aminotransferases and TBL), ECOG PS, vital sign measurements, standard clinical laboratory parameters (hematology, serum chemistry, and urinalysis), ECG parameters, ECHO/MUGA scan findings, and ophthalmologic findings. AEs and laboratory test results will be coded using the most recent version of MedDRA and will be graded using NCI-CTCAE v5.0.
	
Safety

To evaluate HER3 protein expression in tumor tissue and its relationship with efficacy
	
Title: Correlation between HER3 protein expression (as determined by HER3 IHC assay) and efficacy
 
Description: Descriptive summary of HER3 status, and a correlative analysis between HER3 protein expression level (as
	
HER3 protein expression in tumor tissue (as determined by IHC) and correlation with ORR, DoR, and PFS
	
Efficacy/Biomarker

Objectives	Outcome Measure	Endpoints	Category
	
determined by HER3 IHC assay) and efficacy
 
Time frame: Efficacy data are collected at baseline, then from the start of study treatment until documented disease progression by BICR, death, lost to follow-up, or withdrawal by the subject. HER3 data are collected at baseline (biopsy).
		

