#### **Electrocardiograms**

12 lead-ECGs will be performed and recorded for every subject as per the SoE (Table 1.1 and Table 1.2). Subjects should rest supine/semi-recumbent for at least 10 minutes prior to the ECG.

The same test must be used for Screening, EOT, and as clinically indicated. Assessment for the EOT Visit may be performed with a window up to 7 days. At any visit during which a subject exhibits a heart rate  $\leq 50$  bpm or other clinical indications for ECG, the ECG will be repeated. Abnormal, clinically relevant findings occurring post-baseline will be reported as AEs.

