## **Vital Signs**

Descriptive statistics will be provided for the vital sign measurements and changes from baseline by scheduled time of evaluation, including the EOT Visit. A listing of vital sign data will be generated.

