## **Other**

Listings of all other safety data (eg, physical examination findings including ECOG PS, ECHO/MUGA, and ophthalmologic findings) will be generated.

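### Table 3.1 promises descriptive statistics for ECG, ECHO/MUGA, eye, ECOG PS and urinalysis endpoints, but Section 9.5.2 plans listings or names no summary, so measured change that never becomes an adverse event goes untabulated

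*Combined protocol and SAP*

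**What the plan says.** In Table 3.1, and in the same row of the synopsis, the safety outcome is described as "Descriptive statistics of safety endpoints". The endpoint column names ECOG PS and urinalysis and also "ECG parameters, ECHO/MUGA scan findings, and ophthalmologic findings". A footnote adds: "Although this is a secondary objective, this is a primary outcome measure".

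Section 9.5.2 then sets the output by type of data:

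- Laboratory: "Descriptive statistics will be provided for selected clinical laboratory test results (hematology and chemistry) and changes from baseline by scheduled time of evaluation", with a CTCAE-grade shift table for selected tests and a listing of abnormal results. Urinalysis is not mentioned.
- Vital signs: "Descriptive statistics will be provided for the vital sign measurements and changes from baseline by scheduled time of evaluation, including the EOT Visit", plus a listing.
- ECG: "A listing of ECG data will be provided".
- Everything else: "Listings of all other safety data (eg, physical examination findings including ECOG PS, ECHO/MUGA, and ophthalmologic findings) will be generated".

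For abnormal ECGs, Section 8.4.4 says: "Abnormal, clinically relevant findings occurring post-baseline will be reported as AEs".

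**The concern.** A listing shows one subject's values after another. It is not a descriptive statistic, and it gives no denominator, rate or distribution. Section 9.5.2 itself treats the two as different outputs, since vital signs get both. Five components of an outcome labelled primary are therefore promised a summary in one place and given a listing, or no named output, in the other.

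What is at stake is whether the report can state, for each regimen, how many assessed subjects had a measured fall in LVEF, a prolonged QTcF or a new eye finding. The regimens differ in dose (5.6 mg/kg fixed against titration up to 6.4 mg/kg), Section 9.1 calls for analyses by arm, and Table 6.4 already grades LVEF and QTcF change. A programmer following the ECG and Other paragraphs literally would produce none of these counts.

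**Working it through.** The plan states no figure on this point, so the check compares passages.

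**Step 1. Endpoint, schedule and output side by side** (Table 3.1; Tables 1.1 and 1.2; Section 9.5.2).

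| Table 3.1 endpoint | Scheduled after baseline | Output stated in 9.5.2 |
|---|---|---|
| Vital signs | Every cycle, EOT, 40-day visit | Descriptive statistics, change from baseline, listing |
| Hematology, chemistry | Every cycle, EOT, 40-day visit | Descriptive statistics, change from baseline, grade shifts for selected tests |
| ECG | EOT | Listing |
| ECHO/MUGA | EOT | Listing |
| Ophthalmologic | EOT (40-day visit if abnormal at discontinuation) | Listing |
| ECOG PS | Every cycle, EOT, 40-day visit | Listing |
| Urinalysis | EOT | Not named |

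The first two rows match Table 3.1. The other five do not.

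**Step 2. Which measured changes still reach a table.** The route is the adverse event record.

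- Section 8.4.1 makes an isolated ECG abnormality an AE if it is symptomatic, needs corrective treatment, leads to dose reduction or discontinuation, or is an AE in the investigator's judgment.
- Section 10.5.1 extends the judgment of clinical relevance to other safety assessments.
- Section 6.5 requires every dose modification to be recorded on the AE page.
- Section 9.5.2 summarizes treatment-emergent AEs by term, worst grade and action taken, and Section 9.1 makes this by arm.

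A QTcF or LVEF change that is judged drug-related and leads to a delay under Table 6.4 is therefore recorded as an AE and tabulated.

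**Step 3. Which do not.** Two groups can escape if they are asymptomatic, untreated and not judged clinically relevant.

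- LVEF changes for which Table 6.4 continues the drug: a fall of 10% to 20% (absolute) with LVEF above 45%, or LVEF of 40% to 45% with a fall below 10%. With no dose modification, recording as an AE rests on investigator judgment.
- Changes first seen at EOT. Under the Table 1.2 footnote this visit follows the final dose, or the decision to stop, so the finding can no longer trigger a dose modification. EOT is also the only scheduled post-baseline ECG, ECHO/MUGA and routine eye examination.

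These would appear only in listings.

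**Step 4. What a summary would add, as an illustration.** For zero events in n assessed subjects, the exact two-sided 95% upper limit is 1 − 0.025^(1/n).

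- n = 210 (the planned arm size, all with baseline and EOT values): 1 − 0.025^(1/210) = 1.74%.
- n = 150 (assumed): 1 − 0.025^(1/150) = 2.43%.
- n = 100 (assumed): 1 − 0.025^(1/100) = 3.62%.

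For 10 of 210 (4.8%), the exact interval is 2.3% to 8.6%. The documents give neither the expected event rate nor the share of subjects who will have an EOT test. These numbers therefore show the precision a table could report, not the size of an error.

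**The case against.** The strongest reply is that Section 9.5 calls itself a summary and leaves detail to a separate SAP, to be final before database lock and not in the file reviewed. That SAP could add every table wanted here. The opening of Section 9.5.2 also says safety analyses are in general tabular with summary statistics, Section 9.1 provides for counts and percentages, and neither listing paragraph says that only a listing will be made. Much of this stands: the missing tables are an inference from the plan's wording, and the SAP is a proper place to cure it. It does not remove the conflict. The general sentences name none of these measures, while the specific paragraphs name them and state a weaker output than the neighbouring paragraphs do.

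A second reply is that AE reporting already catches what matters. That holds for changes that are symptomatic, treated, lead to dose modification or are judged relevant, and it makes the gap much smaller than the listing paragraphs alone suggest.

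A third is that sparse testing limits any table. Apart from Screening and EOT, ECG and ECHO/MUGA are done only when clinically indicated, so a worst-value summary mixes scheduled tests with tests prompted by symptoms. This is correct and shapes the fix.

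A fourth is that a count of zero can be read off a listing. It can, but a listing supplies neither the number assessed nor an interval.

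**Conclusion.** The inconsistency is real and minor. Table 3.1 and Section 9.5.2 state different outputs for ECG, ECHO/MUGA, ophthalmologic findings, ECOG PS and urinalysis, and should be reconciled. As written, measured change in LVEF, QTcF or eye findings that is not recorded as an AE has no by-arm summary. Its frequency cannot be estimated from the documents. No efficacy result or decision rule is touched.

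Two stronger readings are not supported. A reader might infer that the report will contain no by-arm rates of cardiac or ocular toxicity. It will, through the treatment-emergent AE tables. A reader might also infer that Section 9.5.2 finally fixes the output, so that the summaries can never appear. It does not, because a SAP is still to come. Nor is the 1.7% limit a measured consequence. It assumes 210 evaluable subjects in an arm, whereas missing EOT tests, or an arm halted early under Section 4.1.1, would leave fewer.

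**What to change.** In Section 9.5.2, or in the SAP with a cross-reference, add the following by arm, in subjects with both a baseline and a post-baseline value, as Section 9.1 already requires for change from baseline:

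1. LVEF and QTcF: change from baseline to EOT.
2. LVEF: counts in the Table 6.4 categories, with a remainder category for subjects in none of them. QTcF: counts at 501 ms or more and, separately, with a change above 60 ms. These serve only as analysis categories and imply nothing about dosing.
3. Ophthalmologic findings: shift from baseline to EOT.
4. ECOG PS and urinalysis: shift from baseline to EOT. ECOG PS is recorded every cycle, so a worst-value shift is also well defined.

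Report the number assessed beside each count. Label any worst post-baseline summary of ECG, LVEF or eye findings as including unscheduled, clinically indicated tests. State how EOT values taken after the 47-day on-treatment window are handled. Keep the listings as support.

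The alternative is to amend Table 3.1 to say these items are only listed. That removes the conflict but gives up the summaries.

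The cost is a few extra tables. The data are already collected, and no procedure, visit or efficacy analysis changes.

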## **Vital Signs**

Descriptive statistics will be provided for the vital sign measurements and changes from baseline by scheduled time of evaluation, including the EOT Visit. A listing of vital sign data will be generated.

## **Other**

Listings of all other safety data (eg, physical examination findings including ECOG PS, ECHO/MUGA, and ophthalmologic findings) will be generated.

### **9.5.3. Other Analyses**

The following other analyses are planned in this study.

## **Pharmacokinetics**

Serum concentrations for intact patritumab deruxtecan ADC, total anti-HER3 antibody and released payload MAAA-1181a will be listed, plotted, and summarized using descriptive statistics at each time point of each dosing arm using the PK Analysis Set.

The Population PK (PopPK) analysis to evaluate the effect of intrinsic and extrinsic factors of intact patritumab deruxtecan ADC, and if appropriate, total anti-HER3 antibody and released payload MAAA-1181a may be characterized and may also include available PK data from the Phase 1 studies (U31402-A-J101 and U31402-A-U102). After establishment of the PopPK model, a PopPK/exposure-response model may be developed to evaluate the relationship between exposure and efficacy and toxicity. If conducted, the results of the nonlinear mixed effects PopPK and PopPK/exposure-response models will be reported separately from the CSR.

## **Immunogenicity**

Immunogenicity will be assessed through characterization of prevalence, incidence and titer of ADA. The number and percentage of subjects with treatment-emergent ADA will be calculated. Treatment-emergent ADA positive is defined as subjects who were ADA negative at baseline and became ADA positive (ie, confirmed positive ADA) post-treatment or ADA positive at baseline and post-treatment and had an increase in ADA titer from baseline to post-treatment that meets the cut off value of fold change, or had missing ADA data at baseline and became ADA positive post-treatment.

Concentrations and PK parameters of total anti-HER3 antibody, intact patritumab deruxtecan ADC, and released payload MAAA-1181a may be summarized by status of ADA, if data allows. ADA titer will be determined for samples confirmed ADA positive. When neutralizing antibody assay becomes available, confirmed ADA positive samples may be analyzed for neutralizing activity.

## **Pharmacodynamics**

Not applicable.

## **Biomarker**

Biomarker data include IHC HER3 expression data and genomic alterations data from tumor tissue. HER3 expression data will be summarized and plotted if data permits. HER3 expression and genomic alteration data will be presented in listings. Other biomarker data, if analyzed, may be reported separately (ie, not in the CSR).

## **Inherited Genetics**

A pharmacogenomics analysis may be conducted in combination with data from other studies. If conducted, results of the analysis will be reported separately.

## **9.6. Interim Analyses**

There is no formal interim analysis planned for futility or superiority in this study.

This Phase 2 study will start with 2 randomized dose arms (5.6 mg/kg fixed dose regimen and up-titration dose regimen) with a 1:1 randomization ratio. In the ongoing U31402-A-U102 study, the same population is being studied in multiple expansion cohorts: Cohort 3a and 3b (with 45 subjects planned to be randomized to each dose regimen, 5.6 mg/kg Q3W or up-titration) and Cohort 1 (45 subjects dosed with 5.6 mg/kg Q3W). If, during the conduct of the current trial (U31402-A-U201), analyses from the U31402-A-U102 study indicate that one dose regimen provides clear advantages over the other in terms of benefit/risk, further enrollment into one arm may be discontinued.

## **10. APPENDICES - SUPPORTING DOCUMENTATION AND OPERATIONAL CONSIDERATIONS**

### **10.1. Appendix 1: Regulatory and Ethical Considerations**

#### **10.1.1. Regulatory Compliance**

The study protocol, the IB, available safety information, recruitment procedures (eg, advertisements), subject information and consent form, any subject written instructions to be given to the subject, information about payments and compensation available to the subjects, and documentation evidencing the Investigator's qualifications should be submitted to the independent IRB or EC for ethical review and approval according to local regulations, prior to the study start. The written approval should identify all documents reviewed by name and version.

Changes in the conduct of the study or planned analysis will be documented in a protocol amendment and/or the SAP. Written approval of all protocol amendments and changes to any of the above listed documents must be obtained from the IRB or EC.

The Investigator should notify the IRB or EC of deviations from the protocol or SAEs occurring at the study site and other AE reports received from the Sponsor/CRO, in accordance with local procedures.

The Sponsor will appoint a Coordinating Investigator. Among other possible duties, the Coordinating Investigator will be responsible for reviewing the Final Clinical Study Report and testifying to the accuracy of the description of the study conduct. Because the Coordinating Investigator should have personal knowledge of the conduct of the study, he or she will normally be chosen from among those Investigators who have enrolled and treated at least one subject. However, where an Investigator has special knowledge of the field or of the study, the Coordinating Investigator can be chosen prior to enrollment of the first subject. In all cases, the Coordinating Investigator must be chosen prior to locking the database.

#### **Compliance Statement, Ethics, and Regulatory Compliance**

This study will be conducted in compliance with the protocol, the ethical principles that have their origin in the Declaration of Helsinki, the International Council for Harmonisation (ICH) consolidated Guideline E6 for Good Clinical Practice (GCP) (CPMP/ICH/135/95), and applicable regulatory requirement(s) including the following:

- European Commission Directive (2001/20/EC Apr 2001) and/or;
- European Commission Directive (2005/28/EC Apr 2005) and/or;
- US Food and Drug Administration (FDA) GCP Regulations: Code of Federal Regulations (CFR) Title 21, parts 11, 50, 54, 56 and 312 as appropriate and/or;
- Japanese Ministry of Health, Labor and Welfare Ordinance No. 28 (27 Mar 1997) and/or;

- The Act on Securing Quality, Efficacy and Safety of Pharmaceuticals, Medical Devices, Regenerative and Cellular Therapy Products, Gene Therapy Products, and Cosmetics No. 1 (25 Nov 2014) and/or;
- Other applicable local regulations.

In addition, the Investigator will inform the Sponsor in writing within 24 hours of any urgent safety measures taken by the Investigator to protect the study subjects against any immediate hazard, and of any suspected/actual serious GCP non-compliance that the Investigator becomes aware of.

### **Supply of New Information Affecting the Conduct of the Study**

When new information becomes available that may adversely affect the safety of subjects or the conduct of the study, the Sponsor will inform all Investigators involved in the clinical study, Independent Ethics Committees (IECs)/IRBs, and regulatory authorities of such information, and when needed, will amend the protocol and/or subject information.

The Investigator should immediately inform the subject whenever new information becomes available that may be relevant to the subject's consent or may influence the subject's willingness to continue participation in the study. The communication should be documented on medical records, for example, and it should be confirmed whether the subject is willing to remain in the study.

If the subject information is revised, it must be re-approved by the IEC/IRB. The Investigator should obtain written informed consent to continue participation with the revised written information even if subjects were already informed of the relevant information. The Investigator or other responsible personnel who provided explanations and the subject should sign and date the revised ICF.

#### **10.1.2. Informed Consent**

In obtaining and documenting informed consent, the Investigator should comply with the applicable regulatory requirements, and should adhere to GCP and to the ethical principles that have their origin in the Declaration of Helsinki. The ICF and any revision(s) should be approved by the IEC/IRB prior to being provided to potential subjects.

The subject's written informed consent should be documented in the subject's medical records. The ICF should be signed and personally dated by the subject and by the person who conducted the informed consent discussion (not necessarily the Investigator). The original signed ICF should be retained in accordance with institutional policy, and a copy of the signed ICF should be provided to the subject. The date that informed consent was signed must be recorded in the eCRF.

If the subject cannot read, then according to ICH GCP Guideline, Section 4.8.9, an impartial witness should be present during the entire informed consent discussion. This witness should sign the ICF after the subject has consented to their participation. By signing the ICF, the witness attests that the information in the ICF and any other written information was adequately explained to and apparently understood by the subject and that informed consent was freely given by the subject.

A separate special consent for inherited genetic analysis will be obtained from subjects in accordance with health authorities in their particular region/country.

Suggested model text for the ICF for the study and any applicable subparts (PK, pharmacodynamic, etc.) is provided in the Sponsor's ICF template for the Investigator to prepare the documents to be used at his or her study site. Updates to applicable forms will be communicated via letter from the Sponsor.

For study sites in the US, an additional consent is required for the Health Insurance Portability and Accountability Act (HIPAA).

